**EXPANDED HEMODIALYSIS *VERSUS* ONLINE HEMODIAFILTRATION: A
PILOT STUDY ON INTRADIALYTIC HEMODYNAMICS AND FLUID STATUS**

Institution

Department of Medicine, Renal Division, University of São Paulo, São Paulo,
Brazil

NCT ID NCT03274518

Unique Protocol ID: 16928

Document Date: 09/27/2019

Abstract

Conventional hemodialysis (HD) is essential for the treatment of end-stage renal disease (ESRD) patients, by reducing serum concentration of uremic toxins and correcting fluid overload.

Nevertheless, HD removes almost exclusively low-range uremic toxins. Therefore, medium-range molecules, such as beta-2-microglobulin might accumulate in tissues, leading to many clinical complications, such as neuropathies, tendinopathies, anemia, bone mineral disease and reduced growth in children.

Convective methods might reduce incidence of these complications, by removing molecules of medium-range molecular weight. Online hemodiafiltration (oIHDF) is the most extensively used method in this regard. Nevertheless, there are some barriers to the wider introduction of this method in clinical practice, since specific machines are needed for this procedure, the costs with dialysis lines are higher and water consumption increases. More recently, the development of new membranes for hemodialysis allowed removal of medium- and high-range uremic toxins, with albumin retention. Thus, they allow removal of a broad range of uremic toxins, without changing dialysis machine or increasing water consumption. Such therapy is known as expanded hemodialysis (HDx).

The aim of this present study is to compare the extraction of middle-size molecules, the hemodynamic behavior, fluid and nutritional status of patients submitted to oIHDF or HDx, in a crossover study.

Introduction

End-stage renal disease (ESRD) is a condition characterized by marked decline in renal function, usually at rates below 10 ml/min/1.73 m². In Brazil, there are about 110,000 patients on maintenance hemodialysis (HD) and mortality rates are around 19%.⁽¹⁾ The explanation for this high mortality rate derives from comorbidities such as Diabetes Mellitus, arterial hypertension and left ventricular hypertrophy.⁽²⁻⁴⁾ Additionally, these patients are submitted to extracorporeal circulation, with intense body fluid variation and electrolyte composition during procedure. Besides, several uremic toxins are not removed during HD sessions.⁽⁵⁾

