High cutoff membranes have recently been introduced into clinical practice, with the potential benefit of removing toxins with high molecular weight, typically associated with sepsis, rhabdomyolysis and hematological diseases, such as inflammatory cytokines, myoglobin, free light chains. Such membranes, however, also lead to loss of albumin, which can lead to or aggravate malnutrition.

More recently, membranes with high cutoff values, but with tight pore size distribution have been developed. The main concept is to keep both cutoff and retention onset values close to each other, but with a cutoff value lower than of albumin. This should allow removal of middle-to-high weight range uremic toxins, with very low albumin leak. Thus, these membranes, denominated high retention onset (HRO) membranes, allow performing both diffusive and convective processes in a conventional hemodialysis machine. These new HRO membranes defined a new modality of HD, denominated expanded hemodialysis (HDx).

Hypothesis

Our hypothesis is that HDx is noninferior to olHDF in the following parameters:

- Hemodynamic stability
- Nutritional and fluid status
- Removal of beta-2 microglobulin

Objectives

To evaluate each patient, through a prospective, randomized and cross-over study, the intradialytic hemodynamic behavior, fluid and nutritional status assessed by electrical bioimpedance and B2M removal in two dialytic modalities: HDFol versus HDx.

Subject and Methods

Inclusion criteria

Adult patients who are on maintenance HD at Hospital das Clínicas and agree to participate in the study by signing the informed consent form.

Exclusion criteria

Patients who cannot understand or who refuse to sign the informed consent form;
Patients who are currently on daily HD or olHDF.

Concise methods

a) Clinical and laboratorial data

Clinical data will be collected from the institution's chart, recorded and filled with all necessary precautions to keep confidentiality of patient's information. They are: baseline renal disease, age, history of smoking, sedentary lifestyle, presence of comorbidities such as hypertension and diabetes mellitus, family history of cardiovascular disease, history of coronary and cerebrovascular disease and medications.

Laboratory tests used to determine the biochemical, hematological and bone mineral profile characteristics will be obtained from routinely collected

exams. Such exams are processed by the Central Laboratory of Hospital das Clínicas / FMUSP.

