Blood samples will be collected pre-session, mid-session and post-dialysis sessions, both in the first and last dialysis sessions of each of the periods studied (HDFol or HDx). Pre-session blood samples will be collected immediately after arteriovenous fistula puncture and the middle and post-session samples will be collected from the arterial line, 2 minutes after reduction of blood flow to 50 ml/min and suspension of dialysate flow and/or replacement.

In addition, partial and homogeneous collection of the effluent will be performed by a drainage hose, with an infusion pump operating continuously at a rate of 1l/h, as previously validated in the literature,(22-25) and successfully replicated by our service.(26, 27) The whole effluent of dialysis session will be collected.

Description of study design and procedures are described in figure 1. Blood and effluent samples to be collected are depicted in table 1.

[figure not shown]

Figure 1. Protocol description

Table 1. Description of Serum and effluent samples

Blood	First Sample (pre-dialysis)	Second Sample (mid-dialysis)	Third Sample (post-dialysis)
Albumin	X	X	X
β 2-microglobulin	X	X	X
Creatinin	X		X
Phosphorus	X	X	X
Hematocrit	X		
Hemoglobin	X		
Total Protein	X	X	X
Urea	X	X	X
Effluent			
Albumin		X	
β 2-microglobulin		X	
Phosphorus		X	
Urea		X	

Statistical Analysis

According to parametric distribution or not of the studied variables, paired t test or Wilcoxon's test will be used, respectively. The following variables will be compared in the two following situations HDFol *versus* HDx, HDFol *versus* high-flux HD and HDx *versus* high-flux HD:

- Pre-dialysis serum samples: albumin, β 2-microglobulin, creatinine, phosphorus, hematocrit, hemoglobin, total proteins, urea;
- Intradialytic serum samples: albumin, β 2-microglobulin, phosphorus, total proteins, urea;
- Post-dialysis serum samples: albumin, β 2-microglobulin, creatinine, phosphorus, total proteins, urea;
- Intradialytic effluent samples: albumin, β 2-microglobulin, phosphorus, total proteins, urea;
- Pre-dialysis hemodynamic variables: blood pressure, cardiac index;
- Post-dialysis hemodynamic variables: blood pressure, cardiac index, systolic volume, peripheral vascular resistance;
- Pre-dialysis bioimpedance variables: extracellular water / total body water ratio and α -angle;
- Post-dialysis bioimpedance variables: extracellular water / total body water ratio and α -angle.

References

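### The HDx versus olHDF noninferiority hypothesis spans three domains, but no deciding variable or session is named in any of them

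*Combined protocol and SAP*

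**What the plan says.** The Hypothesis section is framed as noninferiority for one pair of treatments: "Our hypothesis is that HDx is noninferior to olHDF in the following parameters". Three domains follow: hemodynamic stability, nutritional and fluid status, and beta-2 microglobulin removal.

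The Statistical Analysis section prescribes a paired t test or Wilcoxon's test according to distribution. It then says "The following variables will be compared in the two following situations", but lists three contrasts: HDFol versus HDx, HDFol versus high-flux HD, and HDx versus high-flux HD. Eight groups of variables follow, for example "Pre-dialysis serum samples: albumin, β 2-microglobulin, creatinine, phosphorus, hematocrit, hemoglobin, total proteins, urea", "Intradialytic effluent samples: albumin, β 2-microglobulin, phosphorus, total proteins, urea" and "Pre-dialysis hemodynamic variables: blood pressure, cardiac index".

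The title puts hemodynamics and fluid status in front and calls the study a pilot. The Abstract opens its aim differently: "The aim of this present study is to compare the extraction of middle-size molecules".

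The text names no primary variable, significance level, multiplicity rule, noninferiority margin or sample size. Blood is drawn in both the first and the last session of each period (Blood and Effluent samples), and the analysis section does not say which session counts.

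**The concern.** A noninferiority hypothesis needs a stated quantity on which it succeeds or fails. Here each domain has several candidates that can disagree.

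- **Beta-2 microglobulin removal.** Serum is listed before, during and after dialysis, and effluent is listed as well. None of the four is identified as the measure of removal.
- **Hemodynamic stability.** Six variables are listed as separate start or end values. No change within the session is listed, although that is the natural reading of stability.
- **Nutrition and fluid.** There are four bioimpedance entries, and serum albumin or total protein could also be put forward as nutritional.

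Two analysts following the plan could reach opposite conclusions from the same data, by two separate routes. Many difference tests raise the chance that one shows a difference by luck, which could be read as HDx being worse or better. And without a deciding variable or a margin, a non-significant test can be chosen and presented as noninferiority.

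**Working it through.** The plan states no error rate or sample size, so it has no figure to reproduce. The inputs are counts from the Statistical Analysis section plus an assumed two-sided 5% level per test with no adjustment.

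**Listed variables**

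| Group | Count |
|---|---|
| Serum, pre-dialysis | 8 |
| Serum, intradialytic | 5 |
| Serum, post-dialysis | 6 |
| Effluent | 5 |
| Hemodynamic, pre | 2 |
| Hemodynamic, post | 4 |
| Bioimpedance, pre | 2 |
| Bioimpedance, post | 2 |

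Total: 8 + 5 + 6 + 5 + 2 + 4 + 2 + 2 = 34. Over three contrasts: 34 × 3 = 102 listed comparisons. Those involving high-flux HD: 34 × 2 = 68. That leaves 34 for HDx versus olHDF.

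**Variables in the three domains (my mapping).** Hemodynamic 2 + 4 = 6; bioimpedance 2 + 2 = 4; beta-2 microglobulin 4 (three serum times and effluent). Total 14. Counting serum albumin and total protein at three times each as nutritional would add 6.

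**Expected false differences if there is no true difference.** 34 × 0.05 = 1.7 and 14 × 0.05 = 0.7. These expectations do not depend on correlation.

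**Chance of at least one false difference.** Under independence it is 1 − 0.95^k:

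- k = 34: 1 − 0.95^34 = 0.825
- k = 14: 1 − 0.95^14 = 0.512

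The variables are correlated, so I also simulated normal test statistics with a common pairwise correlation (50,000 runs, cut-off 1.96). At zero correlation this gave 82.4% and 50.8%, in line with the formula.

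| Correlation between variables | 34 tests | 14 domain tests |
|---|---|---|
| Independent (formula) | 82.5% | 51.2% |
| 0.3 | 70% | 44% |
| 0.5 | 54% | 35% |
| 0.8 | 26% | 19% |

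The counts could also be higher. Testing the first and last sessions separately would add up to 8 + 5 + 6 = 19 serum tests to this contrast, and blood pressure may mean more than one measure.

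**The other direction.** With N and effect both assumed, a single paired t test at two-sided 5% misses a true difference of 0.5 SD with probability 71% at N = 10, 44% at N = 20, 25% at N = 30 and 13% at N = 40. In a small study, a non-significant result is therefore easy to find and says little about noninferiority.

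**The case against.** The strongest reply is that the plan is narrower than its list suggests, and much of that stands.

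- A reader might infer that the noninferiority claims rest on 102 unadjusted tests, with a 99.5% chance of a false finding (1 − 0.95^102). The documents do not support this. The hypothesis concerns HDx versus olHDF only, so 68 of the 102 comparisons do not bear on it. The 99.5% also needs independence, which is implausible: the same analytes are measured repeatedly, hemoglobin goes with hematocrit, and peripheral resistance is calculated from pressure, stroke volume and heart rate.
- Nor is it established that 102 tests can be run. Blood sampling and hemodynamic readings are described only for olHDF and HDx, and no effluent collection under high-flux HD is described. Figure 1 was not available in the text reviewed and may fill some of these gaps.
- A reader might also infer that nothing ties variables to domains. That is too strong. The Objectives assign fluid and nutrition to bioimpedance, and the Bioelectrical impedance section treats the α-angle as a nutritional marker. The beta-2 microglobulin and hemodynamic rows point to their own domains. What is missing is the single deciding variable and session within each.
- The Objectives already name the two modalities to be compared, so the main contrast is nearly explicit. The different order of topics in the title and Abstract is weak evidence of unclear priority.
- That the tests are unadjusted is inferred from silence.
- Multiplicity explains false differences. A false noninferiority conclusion comes mainly from reading a non-significant difference test without a margin, which is a separate defect.

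The pilot label would excuse a purely exploratory analysis. It does not excuse a noninferiority hypothesis with nothing named to decide it.

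**Conclusion.** The point holds in this form: within the one contrast that tests the hypothesis, none of the three domains has a named deciding variable or session. At an assumed two-sided 5% level without adjustment, the chance of at least one false difference lies between 26% and 82.5% for all 34 variables and between 19% and 51% for the 14 domain variables, over correlations from 0.8 down to independence. It is material even at the narrowest count and strongest correlation examined. The risk of selecting a non-significant result as evidence of noninferiority comes on top; its size depends on a sample size and true effect that the documents do not give.

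The mapping to 14 variables is a judgment, and the correlation range is assumed.

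**What to change.** Before the data are analysed:

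1. Name HDx versus olHDF as the main contrast, and correct the count of contrasts in the Statistical Analysis section.
2. Name one deciding variable and one session per domain, from measurements already planned. Examples are the start-to-end change in blood pressure, one bioimpedance variable, and beta-2 microglobulin mass removed in effluent in the last session of each phase. Mass is concentration times total effluent volume, so confirm that the volume is recorded and that effluent is collected in that session; the text does not specify the sessions.
3. If the bioimpedance variable is the ratio of extracellular to total body water, limit that claim to fluid status, or add the α-angle for nutrition. First reconcile the timing: the Bioelectrical impedance section schedules measurement before the study and before each phase, while the analysis list includes post-dialysis values.
4. Report each deciding variable as a paired difference with a 95% confidence interval. Then either judge each against a prespecified noninferiority margin, requiring all of them for an overall claim so that no alpha split is needed, or drop the noninferiority wording and report estimates only. Without a margin, requiring all of them decides nothing.
5. Report every other variable and contrast as an exploratory estimate with no significance claim.

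The cost is mainly wording, plus the work of justifying margins if the noninferiority claim is kept and of settling the bioimpedance timing. No extra patients are needed to name the variables. The downsides are fewer formal claims and lower power for an overall claim that requires every domain. This is a cheap improvement.

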b) Dialysis

All dialysis procedures will be performed by the Dialog+ Admea™ machine (BBraun Melsungen AG, Germany).

The oHDF will be prescribed as follows: blood flow 350 - 400 ml/min, dialysate flow 800 ml/min, post-dilution flow (90-100 ml/min), with high-flux Xevonta™ (BBraun Melsungen AG, Germany) or CAHP/DICE™ (Baxter Healthcare Corporation, Deutschland) dialyzers, with surface area of 1.7-2.4 m². The duration of each session will be from 3,5h to 4h, depending on current dialysis prescription. Total substitution volume will be higher than 20 L per session.

HDx will follow the same prescription of oHDF, regarding blood and dialysate flows and dialysis duration. There will be no substitution volume. Theranova™ dialyzers (Baxter Healthcare Corporation, Deutschland) will be used for each session.

Before initiating protocol and during the washout period, patients will be submitted to high-flux HD, which is the standard treatment in our service.

c) Hemodynamic monitoring

Cardiac output index (CI), stroke volume (SV - integrated mean of the flow waveform between the current upstroke and the dichotic notch), peripheral arterial resistance (PAR - ratio of mean arterial pressure to stroke volume multiplied by heart rate) and blood pressure (BP) will be accessed by finger beat to-beat monitor Finometer™ (Finapres Medical Systems BV, Arnhem, The Netherlands), within 15 minutes after starting oHDF or HDx sessions (predialysis) and again, 15 minutes before its end (post-dialysis), according to a previous studies of our group.(18-20).

d) Bioelectrical impedance

Segmental tetrapolar bioelectrical impedance (BIS) will be performed in all patients while recumbent, before starting study protocol and before each phase of the study (HDx or oHDF), by the multifrequency InBody™ S10

(Biospace Co., Ltd., Korea) device. It allows assessment of the following parameters regarding body fluids: total body water, total extracellular body water, lower limbs total water content, lower limbs extracellular water content. Additionally, α -angle, which is a marker of cellular integrity and nutritional status, will be noted.(21)

e) Blood and Effluent samples

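### The planned comparisons do not match the described sampling: no on-treatment HDx–HDFol bioimpedance pair, no stated session for pre-dialysis serum, and no described high-flux value for 20 of 34 listed entries

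*Combined protocol and SAP*

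**What the plan says.** The Hypothesis section reads "Our hypothesis is that HDx is noninferior to olHDF in the following parameters" and lists hemodynamic stability, nutritional and fluid status, and removal of beta-2 microglobulin. The Objectives section likewise names two modalities: "fluid and nutritional status assessed by electrical bioimpedance and B2M removal in two dialytic modalities: HDFol versus HDx". High-flux HD appears in neither.

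The Statistical Analysis section is wider. Variables are to be "compared in the two following situations HDFol *versus* HDx, HDFol *versus* high-flux HD and HDx *versus* high-flux HD", by paired t test or Wilcoxon's test, so each comparison needs a value from the same patient under both modalities. The list includes bioimpedance both before and after dialysis.

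The Concise methods describe when data are taken:

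- Part b) places high-flux HD outside the two study phases: "Before initiating protocol and during the washout period, patients will be submitted to high-flux HD".
- Part c) takes hemodynamic readings "within 15 minutes after starting oHDF or HDx sessions (predialysis) and again, 15 minutes before its end (post-dialysis").
- Part d) takes bioimpedance "before starting study protocol and before each phase of the study (HDx or oHDF").
- Part e) takes blood before, midway through and after dialysis, "both in the first and last dialysis sessions of each of the periods studied (HDFol or HDx"). The effluent paragraph follows and names no modality.
- Part a) adds a general source: "Laboratory tests used to determine the biochemical, hematological and bone mineral profile characteristics will be obtained from routinely collected" exams. It gives no list of analytes and no sampling times.

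Part e) refers to Figure 1 for the design and procedures. That figure was not available to this review.

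**The concern.** A paired test can only be run where both members of the pair are measured, and it only answers the question if each member reflects the modality it is labelled with. Three parts of the plan fall short on the text.

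The most serious is bioimpedance, because it affects the randomized comparison of HDx with HDFol and is the stated measure of fluid and nutritional status. Readings taken before a phase begins say nothing about that phase. If two such readings both reflect high-flux HD, they will tend to agree whatever HDx and HDFol do. Under a noninferiority hypothesis, that agreement could be taken as support.

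The second is pre-dialysis serum, where the choice of session decides whether the sample reflects the modality at all.

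The third is the pair of high-flux contrasts. Many of their entries have no described high-flux value. Any that can be run are non-randomized before-after comparisons, yet the plan gives them the same standing as the randomized contrast.

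**Working it through.** The documents give no figure to reproduce here. The check matches each entry in the Statistical Analysis list to the sampling in parts a) to e) of the Concise methods and to Table 1.

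| Group in the SAP list | Entries | On-treatment HDx–HDFol pair described? | High-flux value described? |
|---|---|---|---|
| Pre-dialysis serum | 8 | Yes, from the last session | None named; first-session sample or routine exams possible |
| Mid-session serum | 5 | Yes | No |
| Post-dialysis serum | 6 | Yes | No |
| Effluent | 5 | Yes if it follows the blood schedule, except total proteins (not in Table 1) | No session named |
| Pre-dialysis hemodynamics | 2 | Yes, early in the session | None named; taken after the HDx or HDFol session has begun |
| Post-dialysis hemodynamics | 4 | Yes | No |
| Pre-dialysis bioimpedance | 2 | No | None named; a pre-protocol or pre-phase reading is possible |
| Post-dialysis bioimpedance | 2 | No | No post-dialysis reading described for any modality |

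**Counts.**

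- Total entries: 8 + 5 + 6 + 5 + 2 + 4 + 2 + 2 = 34.
- Entries with no described high-flux value: mid-session serum 5 + post-dialysis serum 6 + effluent 5 + post-dialysis hemodynamics 4 = 20.
- If effluent collection is not limited to HDx and HDFol sessions: 20 − 5 = 15.
- Remaining entries: 34 − 20 = 14 (serum 8, hemodynamics 2, bioimpedance 4). No high-flux comparator is named for any of them.
- Each entry has two high-flux contrasts, so 2 × 20 = 40 of the 2 × 34 = 68 high-flux comparisons have no described high-flux side (2 × 15 = 30 on the wider effluent reading).

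The bioimpedance entries are left out of the 20. Part d) does not say where a reading falls relative to a dialysis session, so a pre-phase reading might serve as a high-flux value.

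**Bioimpedance, HDx versus HDFol.** The scheduled readings are before the protocol, before phase 1 (possibly the same reading) and before phase 2, so 2 or 3 per patient. There are two cases for the phase-2 reading:

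- *Taken after washout.* Both pre-phase readings follow high-flux HD, and neither modality has an on-treatment reading.
- *Taken before washout.* The reading reflects the first modality only, and the second modality has none.

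In both cases the number of within-patient on-treatment HDx–HDFol pairs is 0.

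**Pre-dialysis serum, HDx versus HDFol.** The pre-session sample is drawn straight after fistula puncture. In the first session of a period it therefore precedes any exposure to that period's modality and reflects the high-flux HD given before it. Assuming little carry-over (the text gives no washout length), the expected HDx–HDFol difference in first-session values is close to zero for all 8 entries, whatever the true effect. The last-session sample does follow exposure. The SAP does not say which is used.

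**Mid-session, post-dialysis, effluent and hemodynamic variables.** These are taken once a session is running, so first and last sessions are both on treatment. What is missing is a statement of which session or sessions are used. Part c) also does not say which sessions of a phase are monitored.

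**The case against.** The strongest reply is Figure 1. The protocol sends the reader there for design and procedures, and the SAP's mention of high-flux contrasts and post-dialysis bioimpedance suggests such measurements may be scheduled in it. This stands as a limit: nothing here shows that the readings were never planned or taken. It does not remove the need to reconcile the text, since part d) gives a bioimpedance schedule that does not support the SAP list.

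The effluent paragraph does not repeat the restriction to HDFol or HDx periods. That also stands, and is why 15 is given beside 20. Routine exams might supply some high-flux serum values, but part a) ties them to patient characteristics and neither lists analytes nor gives mid- or post-session times.

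It can also be said that this is a pilot, that HDFol versus HDx is listed first, and that it is the only stated hypothesis. Pilot status excuses imprecision. It does not excuse a comparison with no described data, or one whose readings do not reflect the modalities compared.

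Finally, the 34 are variable-by-timepoint entries. The distinct measures number 19 (8 serum, 5 effluent, 4 hemodynamic, 2 bioimpedance).

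**Conclusion.** On the text, the concern holds in three parts:

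- The 4 bioimpedance entries have no within-patient on-treatment HDx–HDFol pair, so they cannot answer the fluid and nutritional status hypothesis and may falsely suggest no difference.
- The 8 pre-dialysis serum entries are open to the same false reassurance if first-session values are used, and the plan does not rule that out.
- Of the 34 entries, 20 have no described high-flux value (15 on the wider effluent reading), and no high-flux comparator is named for the others.

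This assumes that Figure 1 adds no visits and, for the serum point, that carry-over is small.

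Three stronger readings are not supported. A reader might infer that 20 is a firm minimum, but the effluent wording leaves room for 15. A reader might infer that no bioimpedance entry could ever form a high-flux pair. If the phase-2 reading precedes washout, however, the pre-dialysis entries have one for each patient's first modality. A reader might also infer that every variable should use last-session values only. That would discard valid on-treatment first-session data for mid-session and post-dialysis samples; the problem of a sample taken before exposure concerns pre-dialysis serum.

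The plan should be corrected. Confidence is medium because of the missing figure.

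**What to change.** 1. Reconcile part d) with the bioimpedance comparisons in the SAP. Either take pre- and post-dialysis readings with the existing device at the last session of each phase or, if data collection is over and no such readings exist, remove the HDx–HDFol bioimpedance comparisons and limit the fluid and nutritional conclusion accordingly.
2. Use last-session values for HDx versus HDFol in pre-dialysis serum. For mid-session serum, post-dialysis serum, effluent and hemodynamics, state which session or sessions are used.
3. Drop the high-flux contrasts for variables with no high-flux measurement or, if Figure 1 schedules one, name that session in the methods and the SAP. Report any retained high-flux contrast as a non-randomized before-after comparison with a named comparator.
4. Correct the count of situations in the SAP sentence, and reconcile effluent total proteins (in the SAP list, absent from Table 1).

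**Cost.** Keeping the bioimpedance comparisons adds up to 2 readings × 2 phases = 4 non-invasive readings per patient, at sessions already planned. Removing them adds no measurements but gives up the bioimpedance evidence on fluid and nutritional status. Fewer comparisons with high-flux HD will remain. Keeping effluent total proteins means one more assay per collection, up to 2 sessions × 2 periods = 4 per patient if effluent follows the blood schedule. The rest is wording.

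### Removal of beta-2 microglobulin is a noninferiority hypothesis, but the analysis list names no removal measure; the within-patient reduction ratio should be the stated main variable

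*Combined protocol and SAP*

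**What the plan says.** The Hypothesis section lists "Removal of beta-2 microglobulin" among three parameters on which HDx is expected to be noninferior to olHDF. The Objectives section repeats it as a comparison of the two modalities. No margin is stated.

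The Statistical Analysis section applies a paired t test or Wilcoxon's test to each listed variable. Beta-2 microglobulin appears four times: as a pre-dialysis, an intradialytic and a post-dialysis serum sample (the last under "Post-dialysis serum samples: albumin"), and under "Intradialytic effluent samples: albumin". No reduction ratio, pre-to-post change, clearance or mass removed is named for any solute, and the effluent entry has no unit or formula.

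Section e) Blood and Effluent samples places blood sampling "both in the first and last dialysis sessions of each of the periods studied". The analysis list does not say which of these sessions is compared. On the washout, section b) Dialysis says: "Before initiating protocol and during the washout period, patients will be submitted to high-flux HD". Figure 1, which describes the design, is not shown, so the position and length of the washout cannot be read.

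Section e) also describes a partial, continuous collection of effluent by a pump at 1 l/h, and then says that all of the session's effluent is collected. The readable text does not mention recording total effluent volume.

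**The concern.** The quantity in the hypothesis has no variable in the analysis. A post-dialysis level is the product of the starting level and the fraction left after the session, so it does not measure removal alone. The pre-dialysis comparison would reveal a large starting difference, but it does not turn a post level into removal.

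Removed mass also scales with the starting level, in the opposite sense. At identical removal efficiency, the modality with the higher starting level shows a higher post level, which reads as less removal, and a larger removed mass, which reads as more. The listed serum and effluent results could then disagree, and no listed variable settles the matter. With no measure and no main session named, the choice among post level, ratio, concentration and mass, and between first and last session, would be left until the data are seen.

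**Working it through.** The documents give no figure to reproduce. The check takes the definitions first and then the effluent arithmetic.

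**Serum.** Let RR be the reduction ratio, so post = pre x (1 - RR).

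- If one modality's starting level is higher by a fraction x at equal RR, its post level is also higher by x.
- With equal starting levels, the same post-level difference would need RR' = RR - x(1 - RR). The apparent loss in ratio is therefore x(1 - RR).

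Apparent difference in ratio, in percentage points (all inputs assumed):

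| Starting difference x | RR 60% | RR 70% | RR 80% |
|---|---|---|---|
| 5% | 2.0 | 1.5 | 1.0 |
| 10% | 4.0 | 3.0 | 2.0 |
| 20% | 8.0 | 6.0 | 4.0 |

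For example, 0.10 x (1 - 0.70) = 0.03, or 3 points.

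**Serum against mass.** Ignoring volume change, mass removed = pre x V x RR. Take assumed values RR = 0.70 and V = 15 L:

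- pre 1.0: post 0.300, mass 1.0 x 15 x 0.70 = 10.5
- pre 1.1: post 0.330, mass 1.1 x 15 x 0.70 = 11.55

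Both rise by 10% while the ratio is unchanged.

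**When starting levels can differ.**

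- *First session of a period.* If the high-flux washout precedes each period, starting levels are equal in expectation. Only chance imbalance and carryover remain.
- *Last session of a period.* The patient has already spent the period on the modality, so a starting difference may itself be a treatment effect. The post level then combines that effect with removal in the session.

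**Effluent.** The inputs from section b) Dialysis are dialysate flow 800 ml/min in both modalities, post-dilution flow 90 to 100 ml/min in olHDF only, and duration 3.5 to 4 h (210 to 240 min). Ultrafiltration is ignored.

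- HDx volume: 0.8 x 210 = 168 L to 0.8 x 240 = 192 L.
- olHDF volume, if substitution is added to the 800 ml/min: 168 + 18.9 = 186.9 L to 168 + 21 = 189.0 L at 3.5 h; 192 + 21.6 = 213.6 L to 192 + 24 = 216.0 L at 4 h.
- Concentration in olHDF relative to HDx at equal mass: 800/890 = 0.899 to 800/900 = 0.889, that is, 10.1 to 11.1% lower.
- If substitution is drawn from the 800 ml/min, volumes are equal and the difference is 0%. If mass is analysed, the difference is also 0%.

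The lowest flow over the shortest session gives 18.9 L, while the same section says: "Total substitution volume will be higher than 20 L per session". Those figures need reconciling, but the range above does not depend on it. At exactly 20 L over 3.5 h the result is 20/188 = 10.6%, which lies inside the range.

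**The case against.** The strongest reply is the design. This is a randomised crossover with a washout on high-flux HD, and each patient is compared with himself or herself. If the washout precedes each period, a paired comparison of first-session post levels is a fair test of modality in expectation, and a ratio there mainly reduces noise. That stands. It does not cover the last sessions, which are also sampled and which the list does not separate from the first.

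A second reply is that nothing is lost: pre- and post-session beta-2 microglobulin are both in Table 1, so the ratio can be computed at any time, and the title calls this a pilot. That also stands. The gap is in the definition of the analysis, not in the serum sampling. Defining the variable afterwards still leaves open which measure and which session answer the hypothesis.

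A third reply concerns effluent. Several references cited for the collection method have titles about quantification, total dialysate volume or mass transfer, which suggests that mass is intended. The statement that all effluent is collected may mean sampling throughout the session. Both readings are plausible, so this part is an ambiguity to clear up and not a demonstrated error.

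**Conclusion.** The point holds in a limited form: removal of beta-2 microglobulin is hypothesised, and no listed variable isolates it. The consequence is small for first sessions after a washout and potentially larger for last sessions. The sizes in the serum table rest on assumed starting differences and ratios. Nothing in the documents makes a particular value likely, and without a margin they cannot say how large a distortion would matter.

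Three stronger readings should be resisted.

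- A reader might infer that the planned serum comparisons are biased. The documents do not support that for first sessions, where randomisation and washout balance the starting levels in expectation, provided the washout precedes each period.
- A reader might infer that the effluent analysis favours HDx by 10.1 to 11.1%. That requires concentrations to be compared and substitution to be added to the 800 ml/min. The plan states neither, and if either fails the figure is 0%.
- A reader might infer that the hemodynamic analysis has the same defect, because stroke volume and peripheral resistance are listed only post-dialysis although they are measured early and late. The paired post-dialysis comparison is valid, and their absence from the pre-dialysis entry is a minor list omission.

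This is a change that should be made. It is inexpensive, and it does not imply that the planned comparisons are invalid.

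**What to change.** 1. Make the within-patient serum beta-2 microglobulin reduction ratio, 1 - post/pre, the main removal variable. Compare HDx with olHDF on it by the planned paired method. Name in advance one main session, the first or the last of each period, and report the other as supportive. Keep the listed level comparisons, since a last-session pre-dialysis difference may itself be a treatment effect.
2. If net ultrafiltration or weight loss (UF) is recorded, report as a sensitivity analysis a ratio corrected for hemoconcentration, 1 - [post x (V - UF)] / [pre x V], with one rule for the distribution volume V in both modalities. Section d) Bioelectrical impedance schedules measurements before the protocol and before each phase, so the rule must not depend on a last-session reading that is not described there.
3. State that effluent results are analysed as mass removed: concentration x total effluent volume, with that volume (not the sampled volume) recorded at each session. Treat mass as secondary, because it also scales with the starting level. Say whether substitution is drawn from or added to the 800 ml/min.
4. Reconcile the description of a partial collection with the statement that all effluent is collected.
5. Add stroke volume and peripheral resistance to the pre-dialysis list, as a minor correction.

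The cost is revised wording, slightly more calculation, recording of total effluent volume and of weight or ultrafiltration, and one added main variable. No extra blood or effluent samples are needed.
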